#### 7.3.5 EARLY TERMINATION VISIT

Not applicable.

#### 7.3.6 UNSCHEDULED VISIT

In case of unplanned medical contact, the prespecified outcomes will be assessed as planned by phone call, and in addition, additional relevant medical data on the type of unplanned medical contact will be identified from the medical file. All suspected bleeding events and reinterventions will be adjudicated by a blinded adjudicator, unaware of the assigned treatment.

#### 7.3.7 SCHEDULE OF EVENTS TABLE

Procedures	Screening	Day 0 Baseline	Day 2 Follow-up	Day 7 Follow-up
Assess inclusion and exclusion criteria	х			
Informed consent	Х			
Randomization	х			
Patient characteristics		Х		
Procedure characteristics		Х		
Study drug administration		Х	x (up to day 3)	
Outcome assessment			Х	Х
Adverse events			Х	Х
Serious adverse events		_	Х	Х

#### 7.4 JUSTIFICATION FOR SENSITIVE PROCEDURES

Not applicable

#### 7.5 CONCOMITANT MEDICATIONS, TREATMENTS, AND PROCEDURES

The use of the concomitant medication will be recorded in the CRF, including:

- Other antithrombotic drugs: aspirin (Asaflow®, Cardio-aspirine®), clopidogrel (Plavix®), ticagrelor (Brilique®), prasugrel (Efient®), dipyridamole (Aggrenox®), LMWH
- Non-steroidal anti-inflammatory drug use (eg. ibuprofen)

#### 7.6 PROHIBITED MEDICATIONS, TREATMENTS, AND PROCEDURES

In patients treated with NOACs, the use of NSAIDs should be limited according to the current standard-ofcare, and is left at the discretion of the treating physician.

#### 7.7 PROPHYLACTIC MEDICATIONS, TREATMENTS, AND PROCEDURES

Not applicable

#### 7.8 RESCUE MEDICATIONS, TREATMENTS, AND PROCEDURES

The treatment of a bleeding event is considered standard-of-care and may include (at the discretion of the treating physician):

- Rinsing the extraction socket, applying hemostatic measures, removal of the false coagulum, stitching
- Interruption of the NOAC when necessary

#### 7.9 PARTICIPANT ACCESS TO STUDY AGENT AT STUDY CLOSURE

TXA 10% mouthwash is commercially available.

#### 8 ASSESSMENT OF SAFETY

#### 8.1 SPECIFICATION OF SAFETY PARAMETERS

In this phase IV study with on-label use of TXA mouthwash, no serious adverse reactions are anticipated.

#### 8.1.1 DEFINITION OF ADVERSE EVENTS (AE)

Any untoward medical occurrence in a subject or clinical investigation subject administered a pharmaceutical product and which does not necessarily have to have a causal relationship with this treatment. An AE can therefore be any unfavorable and unintended sign (including an abnormal laboratory finding, for example), symptom, or disease temporally associated with the use of a medicinal product, whether or not considered related to the medicinal product (ICH E2A Guideline. Clinical Safety Data Management: Definitions and Standards for Expedited Reporting, Oct 1994).

#### 8.1.2 DEFINITION OF SERIOUS ADVERSE EVENTS (SAE)

Any untoward medical occurrence that at any dose:

- Results in death;
- Is life-threatening;
- Requires inpatient hospitalization or prolongation of existing hospitalization;
- Results in persistent or significant disability/incapacity;
- Is a congenital anomaly/birth defect; or
- Is an important medical event.

In addition, suspected transmission of an infectious agent, pathogenic or nonpathogenic are considered a SAE. Although pregnancy, overdose and cancer are not always serious by regulatory definition, these events are handled as SAEs. An overdose is defined as the accidental or intentional administration of any dose of a product that is considered both excessive and medically important.

#### 8.1.3 DEFINITION OF UNANTICIPATED PROBLEMS (UP)

Not applicable.

#### 8.2 CLASSIFICATION OF AN ADVERSE EVENT

#### 8.2.1 SEVERITY OF EVENT

The following definitions will be used to assess intensity of AEs per the NCI CTCAE criteria:

EXTRACT-NOAC Version 1.1
Protocol 5 July 2017

- Grade 1 Mild AE
- Grade 2 Moderate AE
- Grade 3 Severe AE
- Grade 4 Life-threatening consequences; urgent intervention indicated
- Grade 5 Death related to AE

#### 8.2.2 RELATIONSHIP TO STUDY AGENT

Adverse events will be recorded during the follow-up visit at day 7. The relationship to the study agent will be adjudicated:

- Related The AE is known to occur with the study agent, there is a reasonable possibility that the study agent caused the AE, or there is a temporal relationship between the study agent and event.
   Reasonable possibility means that there is evidence to suggest a causal relationship between the study agent and the AE.
- Not Related There is not a reasonable possibility that the administration of the study agent caused
  the event, there is no temporal relationship between the study agent and event onset, or an
  alternate etiology has been established.

#### 8.2.3 EXPECTEDNESS

No adverse events are expected, therefore any adverse event will be unexpected.

# 8.3 TIME PERIOD AND FREQUENCY FOR EVENT ASSESSMENT AND FOLLOW-UP

Adverse events will be assessed at day 2 and 7 follow-up.

#### 8.4 REPORTING PROCEDURES

Following the subject's written consent to participate in the study, all AEs and SAEs, related to the study agent (tranexamic acid, IMP) will be collected.

Although no drugs other than the study agent will be provided by the sponsor to the subjects participating in this interventional study, investigators may become aware of (S)AEs in subjects possibly in relation to marketed drugs as a part of their ongoing therapies. Data on SAEs will be collected, and relatedness of these events to the use of marketed drugs associated with this study (where applicable) will be assessed by the investigator. SAEs determined to be related, including exposure during pregnancy and overdose, will be recorded and reported. A form will be completed for any event where doubt exists regarding its status of seriousness, including overdose and cancer. Reporting of SAEs of marketed drugs will follow regulatory guidelines. Pending on the marketed drug, reconciliation of SAEs cases (case level only) with the manufacturer is indicated. (E.g. for apixaban, frequency of reconciliation is planned every 3 months and

prior to the database lock or final data summary. BMS GPV&E will email, upon request from the Sponsor, Requests the GPV&E reconciliation report. for reconciliation should be [contact]. The data elements listed on the GPV&E reconciliation report will be used for case identification purposes. If the Sponsor determines a case was not transmitted to BMS GPV&E, the case will be sent immediately to BMS. For apixaban, BMS will be contacted at [contact] for SAE. Adverse Events of special interest for apixaban include potential or suspected cases of liver injury, including but not limited to liver test abnormalities, jaundice, hepatitis or cholestasis, regardless of whether the events are classified as serious or unexpected.)

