#### 10.4.4 SAFETY ANALYSES

 The number of non-oral bleeding, allergic reactions and thrombotic complications in the TXA group and placebo group will be compared using the Fisher Exact Test or Chi Square test, depending on the number of events.

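### Section 8.4 limits collection to study-agent-related AEs and SAEs, contradicting 7.3, 8.1.1, 8.2.2 and 8.3; events without their own call question could go unrecorded

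*Combined protocol and SAP*

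**What the plan says.** The protocol is the only analysis document; 10.1 states that there is no separate plan.

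- **8.4, first sentence.** After written consent, "all AEs and SAEs, related to the study agent (tranexamic acid, IMP) will be collected".
- **8.4, second paragraph.** This deals with SAEs possibly linked to marketed drugs that patients already take. SAE data are to be collected and the investigator judges relatedness to those drugs. The following sentence then restricts what is recorded and reported to SAEs found to be related.
- **8.1.1.** An AE is an occurrence "which does not necessarily have to have a causal relationship with this treatment", and the definition repeats "whether or not considered related to the medicinal product".
- **8.2.2.** "Adverse events will be recorded during the follow-up visit at day 7", after which "The relationship to the study agent will be adjudicated" as Related or Not Related. The assessor is not named and blinding is not mentioned.
- **8.3.** "Adverse events will be assessed at day 2 and 7 follow-up". The day-2 and day-7 checklists (7.3.3, 7.3.4) and the schedule table (7.3.7) likewise list AEs and SAEs without a causality condition.
- **10.4.4.** "The number of non-oral bleeding, allergic reactions and thrombotic complications in the TXA group and placebo group will be compared". The safety review after 100 patients (8.5, 10.4.7.1) covers the same three event types.

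**The concern.** A collection rule decides what reaches the database, and an adjudication rule classifies what is already there. The first sentence of 8.4 merges the two: an event must be thought related before it is collected. Two sites could then follow different sections, record different events, and both comply with the protocol.

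An event that was never recorded is hard to recover after a seven-day follow-up. The purpose of recording events regardless of cause is to let the randomised comparison show an imbalance that nobody predicted. That matters here because the protocol starts from a strong prior: 8.1 anticipates no serious adverse reactions and 8.2.3 expects no adverse events at all. A filter applied by people holding that view works against finding the unexpected.

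**Working it through.** The contradiction is textual, so the check sets the sections side by side. The plan states no figure on this point.

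**Step 1. Does 8.4 conflict with the other sections?**

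| Section | Event enters the data if | Causality judged |
|---|---|---|
| 8.1.1 (definition) | it is untoward, whatever the cause | not part of the definition |
| 7.3.3, 7.3.4, 7.3.7, 8.3 | it is reported at the day-2 or day-7 call | not mentioned |
| 8.2.2 | it is recorded (day 7 stated) | after recording |
| 8.4, first sentence | it is related to the study agent | before collection |

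The Not Related category in 8.2.2 begins "There is not a reasonable possibility that the administration of the study agent caused" the event. Under 8.4 no event of that kind would be in the data to classify. Sections 8.2.2 and 8.3 also differ on timing: day 7 alone against days 2 and 7.

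**Step 2. Does the second paragraph of 8.4 repair it?** No. It covers SAEs and marketed drugs, says nothing about unrelated non-serious AEs, and reinstates a relatedness condition for what is recorded.

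**Step 3. Which events are exposed?**

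| Event type | Own question at a call? | Exposed to the 8.4 filter? |
|---|---|---|
| Non-oral bleeding | Yes, day 7 | No |
| Stroke, myocardial infarction, deep vein thrombosis, pulmonary embolism | Yes, day 7 | No |
| Systemic embolism (part of the thrombotic outcome, 4.2.2) | No | Yes |
| Allergic reaction (8.5, 10.4.4) | No | Yes, but usually passes |
| Other AEs and SAEs | No, only the general AE/SAE item | Yes, apart from unplanned contacts and hospitalisations |

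Allergic reactions usually pass because 8.2.2 offers three alternative routes to Related: the event is known for the agent, there is a reasonable possibility, or the timing fits. Section 2.3.1 already lists allergic reaction as a risk of the mouthwash. The screen is still not clean. Timing alone can make an event Related, while an established alternative cause can make the same event Not Related.

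**Step 4. Size.** The documents give no AE rate and no share of events likely to be judged related, so the loss cannot be computed. The following illustration shows direction only. Its one input from the plan is 118 per group (10.5), which reproduces with unpooled variance: (1.960 + 0.842)² × (0.30×0.70 + 0.15×0.85) / 0.15² = 7.849 × 0.3375 / 0.0225 = 117.7, so 118.

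Assume that an event captured only as an AE has true rates of 2% (placebo) and 10% (TXA), and that a share s is judged related in each arm. The recorded difference is s × (10% − 2%). Power is the two-proportion normal approximation at two-sided 5%, which is rough with counts this small.

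| s | Expected events, placebo / TXA | Recorded difference | Approximate power |
|---|---|---|---|
| 1 | 2.4 / 11.8 | 8 points | 0.74 |
| 0.75 | 1.8 / 8.9 | 6 points | 0.61 |
| 0.5 | 1.2 / 5.9 | 4 points | 0.44 |
| 0.25 | 0.6 / 3.0 | 2 points | 0.24 |

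With assumed rates of 2% and 6%, power over the same values of s is 0.35, 0.27, 0.19 and 0.12. A filter acting equally in both arms shrinks any real difference; it does not create one. The collection rule has no bearing on the sample size for the primary outcome.

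**The case against.** The strongest reply is that this is loose drafting. Section 8.4 is headed as a reporting section, whereas data collection is laid out in 7.3.3, 7.3.4, 7.3.7 and 8.3, none of which has a filter. A site working from the call checklists would ask every patient about AEs and SAEs. In addition, both checklists ask about any unplanned medical contact, including hospitalisation, with a reason field that includes death and a free category, so the most serious events would largely surface there whatever their cause. These points limit the harm and stand. They do not remove the conflict, because the sentence in 8.4 speaks of what is collected, not only of what is passed on.

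Three stronger readings are tempting, and the documents support none of them.

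- *The safety comparison rests on the investigator's opinion of causality.* Two of the three event types in 10.4.4 have direct day-7 questions, with systemic embolism the only gap. The investigator is named only for relatedness to marketed drugs; for the study agent, no assessor is named.
- *Events would be lost differently by arm.* The trial is double-blind (4.1). Only the placebo is described as flavoured (6.1.2, 6.1.4) and the success of blinding is not evaluated (10.6.2), but nothing shows that allocation would be recognised.
- *SAEs would vanish from the data.* That needs every SAE to be judged unrelated, which is implausible when timing alone can make an event Related, and it ignores the unplanned-contact items. Nor does 10.4.4 plan an overall SAE comparison that could be lost.

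**Conclusion.** The point holds in a limited form. The first sentence of 8.4 contradicts 8.1.1, 8.2.2, 8.3, 7.3.3 and 7.3.4, and its second paragraph does not resolve the conflict. If the sentence is followed as written, events judged unrelated to the study agent, by an unnamed assessor, stay out of the data unless another question captures them. That affects general AEs and SAEs, systemic embolism and, to a small extent, allergic reactions. Non-oral bleeding, the other thrombotic events and the primary outcome are not affected.

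The expected consequence is under-counting in both arms. The conclusion assumes that at least one site applies 8.4 literally; if all sites work from the checklists alone, little or nothing is lost. The power figures above rest on assumed rates and are not estimates for this trial.

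**What to change.** 1. **8.4:** state that all AEs and SAEs from consent to the day-7 call are recorded for every participant regardless of causality. Use relatedness only to decide onward reporting, and word the marketed-drug paragraph the same way.
2. **8.2.2:** name who assesses relatedness to the study agent and state that it is done blind to allocation. At present, blinded adjudication is specified only for bleeding events and reinterventions (4.2, 7.3.6). Align the timing with days 2 and 7 in 8.3.
3. **7.3.3 and 7.3.4:** add allergic reaction to the call checklist, and add systemic embolism to the existing thrombotic question.
4. **10.4.4:** tabulate all AEs and SAEs by arm, with related events as a subset.

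The cost is small wording edits in 7.3, 8.2.2, 8.4 and 10.4.4, and a few more AE lines per patient at two calls that already include an AE/SAE item. Sample size, visits and the primary analysis do not change.

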#### 8.5 STUDY HALTING RULES AND SAFETY OVERSIGHT

Interim analysis will be performed after inclusion of 100 patients to assess thrombotic events, allergic reaction and non-oral bleeding.

#### 9 CLINICAL MONITORING

Clinical site monitoring is conducted to ensure that the rights and well-being of human subjects are protected, that the reported trial data are accurate, complete, and verifiable, and that the conduct of the trial is in compliance with the currently approved protocol/amendment(s), with GCP, and with applicable regulatory requirement(s).

#### 10 STATISTICAL CONSIDERATIONS

#### 10.1 STATISTICAL AND ANALYTICAL PLANS

There is no external statistical and analytical plan.

#### 10.2 STATISTICAL HYPOTHESES

This is a superiority study. The null hypothesis is that there is no difference in any oral bleeding between the intervention group and the control group (primary outcome).

#### 10.3 ANALYSIS DATASETS

- The primary analysis set of interest will first be the intention-to-treat population (all randomized patients according to their randomized treatment).
- In addition, a sensitivity analysis will be done on the per-protocol population. The per-protocol population is defined as the subjects without major protocol deviations who complied to the assigned treatment for at least 80%. The per-protocol population will be finalized prior to the unblinding of the data.

#### 10.4 DESCRIPTION OF STATISTICAL METHODS

#### 10.4.1 GENERAL APPROACH

- Categorical and continuous data will be presented by randomized treatment group using appropriate summary statistics.
- The overall significance level for the primary endpoint of this study is set at 5% (2-sided). To
  account for the planned interim analysis (see section...), the methods as described by Cui, Hung
  & Wang (1999) will be used to preserve the overall Type I error.
- For the secondary endpoints, no adjustment will be made to the significance level to account for multiple testing.
- For all primary and secondary endpoints, an estimate of the treatment effect and associated 95% confidence interval will be presented. E.g. for the primary endpoint, the risk difference and its 95% confidence interval will be presented.

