#### 10.4.2 ANALYSIS OF THE PRIMARY EFFICACY OUTCOME(S)

The number of bleeding events up to day 7 will be analysed in terms of a risk difference between the two treatment groups, using the methods described by Cui, Hung & Want (1999).

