#### 10.4.3 ANALYSIS OF THE SECONDARY OUTCOME(S)

 The number of all different type of bleeding events, number of reinterventions and number of unplanned NOAC interruptions in the TXA group and placebo group will be compared using the Fisher Exact Test or Chi Square test, depending on the number of events. The effect of treatment will be estimated by the risk difference and presented along with its associated 95% confidence interval.

The procedural bleeding score in the TXA group and placebo group will be compared using the Student ttest of Mann-Whitney U-test, as appropriate. The effect of treatment will be estimated by the difference between treatments and presented along with its associated 95% confidence interval.

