#### 10.4.7.2 EFFICACY REVIEW

After 100 patients have reached their 7-day visit, an efficacy review is planned to reassess the required sample size. This will be done using the methods described by Cui, Hung & Wang (1999). The sample size re-estimation (SSR) will be based on the observed conditional power at the time of the interim analysis. The re-estimated sample size will be required to be between 150 and 300 patients. Full details for the methodology of the SSR will be provided in an Interim Statistical Analysis Plan.

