#### 10.5 SAMPLE SIZE

- Based on the previously cited pilot study, we estimate the rate of the primary outcome at 30% in the placebo group (7).
- We estimate to show an absolute risk reduction (ARR) of 15% This means an incidence of 15% in the tranexamic acid group.
- Confidence level is set to 95%, power is set to 80%.
- Under the above assumptions, in order to have 80% to detect a statistically significant risk difference between treatments, 118 patients per group or 236 patients in total will be required.

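### Does the plan have to spell out how the primary 95% confidence interval is built once the sample size can be re-set to between 150 and 300?

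*Combined protocol and SAP*

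**What the plan says.** All references are to the combined protocol and SAP.

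- **Section 10.4.1, level.** "The overall significance level for the primary endpoint of this study is set at 5% (2-sided"). The Cui-Hung-Wang methods are named as the means of protecting it. The pointer to the interim section is unfinished: "account for the planned interim analysis (see section" is followed only by dots.
- **Section 10.4.1, estimate.** One sentence promises an effect estimate and 95% interval for every primary and secondary endpoint. The example given is that "for the primary endpoint, the risk difference and its 95% confidence interval will be presented".
- **Section 10.4.2.** Bleeding up to day 7 is analysed "in terms of a risk difference between the two treatment groups, using the methods described by Cui, Hung & Want (1999"; the third name is a misprint).
- **Section 10.4.3.** For secondary endpoints, which have Fisher or chi-square tests, the wording is close to that of 10.4.1: "The effect of treatment will be estimated by the risk difference and presented along with its associated 95% confidence interval".
- **Section 10.4.7.2, range.** After 100 patients reach their 7-day visit, the sample size is reassessed from observed conditional power. The new total is bounded: "The re-estimated sample size will be required to be between 150 and 300 patients".
- **Section 10.4.7.2, detail.** The rule itself is left to a further document: "Full details for the methodology of the SSR will be provided in an Interim Statistical Analysis Plan".
- **Section 10.5.** At 30% versus 15%, "118 patients per group or 236 patients in total will be required".

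**The concern.** The Cui-Hung-Wang test fixes the stage weights in advance, whatever second-stage size is chosen. An interval from the combined counts weights each patient equally. The two agree closely when the final total is near 236 and drift apart as it moves away. At 150 the last 50 patients are 33% of the sample but carry 45% of the weighted estimate.

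Because 10.4.1 covers all endpoints in one sentence, and 10.4.3 uses similar words beside ordinary tests, a programmer might put an ordinary interval next to the weighted p-value. The report could then show an interval that excludes zero beside a non-significant primary test. If the construction were chosen after unblinding with a borderline result in hand, readers could doubt the choice.

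**Working it through.** **1. The plan's own figure.** With unpooled variance, n per group = (1.960 + 0.842)² × (0.30×0.70 + 0.15×0.85) / 0.15² = 7.849 × 0.3375 / 0.0225 = 117.7, so 118 per group and 236 in total. This matches section 10.5.

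**2. The weighted test.** The interim is at 100 of 236 (10.4.7.2 and 10.5). The weights are not stated; I assume the usual ones, fixed by the planned stage sizes:

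Z = √(100/236) z₁ + √(136/236) z₂ = 0.651 z₁ + 0.759 z₂, significant if |Z| > 1.96.

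**3. Can the two results conflict?** Take an assumed interim of 17/50 versus 6/50, a cut to 150, then 5/25 versus 5/25.

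- *Ordinary interval:* 22/75 − 11/75 = 14.7 points. SE = √(0.293×0.707/75 + 0.147×0.853/75) = 6.66 points, giving 1.6 to 27.7.
- *Weighted test, arm-pooled variance:* z₁ = 0.22 / √(0.23×0.77×2/50) = 2.61 and z₂ = 0. Z = 0.651 × 2.61 = 1.70, p = 0.089.
- *Weighted test, unpooled variance:* z₁ = 0.22 / √(0.34×0.66/50 + 0.12×0.88/50) = 2.71. Z = 1.76, p = 0.078.

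So a conflict is possible under either variance form. It is sensitive to detail, though. With 7/25 versus 6/25 afterwards, the ordinary interval is 2.6 to 29.4 and the test gives p = 0.052 arm-pooled but p = 0.045 unpooled. The second form, which is the one that reproduces 118, shows no conflict.

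**4. How often?** Exact binomial enumeration of all interim and second-stage outcomes. Assumptions, since the protocol gives none: the weights above, 1:1 allocation in each stage, no early stop for efficacy, the total set to the smallest even number reaching 80% or 90% observed-trend conditional power, several treatments of low conditional power, and both variance forms.

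Chance that the ordinary Wald interval excludes zero while the weighted test is not significant:

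| True rates | N fixed at 236 | N 236-300 | N 150-300 |
|---|---|---|---|
| 30% vs 15% | 0.1-0.5% | 0.1-1.3% | 2.9-5.6% |
| 30% vs 20% | 0.2-0.8% | 0.2-2.4% | 2.4-5.7% |
| 30% vs 30% | at most 0.2% | at most 0.6% | at most 1.5% |

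The first column is not zero because the weighted statistic combines the two stages separately even when the total is unchanged. That part is not caused by re-estimation.

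**5. What would be lost?**

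- Coverage of the ordinary interval at 30% versus 15%: 93.9-94.8%.
- With no effect, the ordinary interval excludes zero in 5.0-6.6% of trials with cuts and 5.2-5.6% without, against 5.3% at fixed 236.
- Type I error of the weighted test: 5.1% arm-pooled, 5.4-5.8% unpooled. It does not depend on which interval is printed.
- An interval obtained by inverting the weighted statistic cannot disagree with the test, and covers 94.3-94.9%.

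**6. Which result decides?** Section 10.2 states the primary null hypothesis. Section 10.4.1 sets the 5% level and assigns its protection to the Cui-Hung-Wang methods. No section makes exclusion of zero by the interval a criterion for success. The weighted test therefore decides.

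**The case for a change.** The strongest case for a change is that the gap is real and cheap to close. Section 10.1 says there is no external SAP, so section 10.4 is the only place certain to specify the final interval. The Interim SAP's stated scope is re-estimation, which probably covers the weights but not clearly the final estimate. Cutting is not a rare branch either: at 30% versus 15% under the assumed rules, the total falls below 236 in 46-55% of trials. Among trials with a non-significant primary test, about 14-28% would show an ordinary interval that excludes zero. Two or three sentences would settle it.

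Part of this stands. The construction is not written out, and an analyst who drafts the Interim SAP would do well to record it. But the case depends on the analyst taking the less natural reading. Section 10.4.2 attaches the named method to the risk-difference analysis itself, not only to a p-value. The similar wording in 10.4.3 concerns endpoints with their own conventional tests, so it says little about the primary one. The conflict rates also require an ordinary interval, a rule that allows cuts, and a true effect near the design value. Reporting both intervals would still leave a visible difference to explain.

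**Conclusion.** No change to the plan follows. What is missing is detail about how an estimate is presented, and the plan's own choice of method points to the sensible way to fill it: an interval consistent with the weighted test. The primary conclusion and its Type I error are the same whichever interval is printed.

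If an ordinary Wald interval were used, the conflict rate would be about 3-6% with cuts to 150 and about 0.1-1.3% without, at 30% versus 15%; with no effect it would be at most 1.5% and 0.6%. These figures rest on assumed weights, conditional-power targets and re-estimation rules, and the Interim SAP that would settle them is not among the documents. Even then, coverage stays close to nominal at the design rates. The unfinished cross-reference in 10.4.1 is a clerical slip; 10.4.7.2 is plainly its target.
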